# 13.10 Patient recruitment and power

The total recruitment time lasts until 31.12 2005. Thereafter a 2-year observation time follows. The study opened 01.01.2001. During the first 2 years approximately only HIT Group patients were included. From the start of the HIT- SIOP PNET 4 protocol patients from all participating countries, Austria, Belgium, Denmark, France, Germany, Italy, Norway, Spain, Sweden, Switzerland, The Netherlands and the United Kingdom will be included. Around 80 patients per year are estimated to be recruited during the last two years of the study. The number of patients lost to follow up will be regarded as negligible.

This study estimates a 3 year EFS of 70 % for patients in the standard RT arm and an expected EFS of 85 % for patients in the HFRT arm. The study should have a power of 90% to answer the main question. The total number of patients needed can be estimated as below. The study aims to recruit 320 patients.

 $P_1$  denotes the calculated probability of 3 year event free survival of the conventional RT and  $P_2$  the corresponding probability of the hyperfractioned RT. In most cases the assumed contribution of a patient to the comparison exceeds 3 years (for a few of them it could be 7 years). The log rank test compares the hazard functions of event for the two treatments during the study period but for the HIT-SIOP PNET 4 Protocol Version 3.0,  $27^{th}$  July 2010 (RG\_10-034)

convenience of interpretation the quantities  $P_1$  and  $P_2$  are used in the figure Two sizes, n=320 and n=242, are considered. The recruitment rate was assumed to be constant for 2.8 years at the level 33.6 patients per year and thereafter constant at the level 102.7 patients per year (the case n=320) and 67.3 patients per year (n=242), respectively. Furthermore it is assumed that the recruitment stopped after 5 years but the study continued 2 more years. The power was determined by simulation. The significance level was 0.040 and only the last occasion of analysis was considered. The hazard functions were assumed to be constant as functions of time, and no loss of follow up was assumed.

The curves 90% power n=320 almost coincided with 80% power n=242. For points  $(P_1, P_2)$  above the curve corresponding to 90% power, e.g., the power is higher than 90%. The line y = x corresponding to equal probabilities was drawn to facilitate the reading of the figure.

### 13.11 Results of the Biological Studies

The results of all biological studies will be collated centrally by [name], Northern Institute of Cancer Research, University of Newcastle upon Tyne, UK, but analysis of these results will depend upon the efficient exchange of data between Newcastle and the International Data Centre in Stockholm. This requires uniformity in the organisation of databases, which will be resolved by the start of the biological studies. The frequency and distribution of each of the molecular aberrations will be analysed. Their relationship to clinical and pathological features will be explored using standard Chisquare and Fisher test analysis. The impact of the presence of any given molecular aberration(s) on EFS and overall survival of patients will also be conducted using Log Rank univariate and Cox multivariate analyses.

# 13.12 Power calculation and statistical analysis of the neurological and endocrine follow-up

The results of all quality of survival studies, including the HUI, SDQ, endocrine and audiological data but excluding the quality of life (QoL) questionnaires, will be collated centrally by [name] at the University of Southampton. QoL questionnaire data will be collated by [name] at the University of Münster. Analysis of these results in Southampton (HUI, SDQ, endocrine and audiology) and Münster (QoL) will depend upon the efficient exchange of data between Southampton and Münster and between these centres and the International Data Centre in Stockholm. [name] will supervise analysis of the endocrine data. This requires uniformity in the organisation of databases in the centres involved, which will be resolved by the start of the collection of quality of survival information.

The measures will provide a longitudinal, prospective description of Health Status and emotional health that is itself of value. However a primary aim is to compare the quality of outcome between the two treatment arms and hypotheses relate to an effect of treatment allocation on cognition, hearing, behaviour, growth and reproductive health.

# **Secondary Endpoints relating to Outcome**

We aim to test the hypothesis that treatment allocation influences cognition, hearing, behaviour, growth and/or reproductive health. The size of the groups in each of the two treatment arms is planned to be 160 children. Assuming event free survival of 75 % and 10 % loss of these survivors to follow-up, the percentage difference between prevalence of outcomes among ascertained survivors in the two HIT-SIOP PNET 4 Protocol Version 3.0, 27th July 2010 (RG\_10-034)

treatment arms that the study would have 80 % power to detect at P<0.05 is:

Outcome in ascertained survivors (n=213)	Overall % prevalence (both arms)	% difference	Numbers affected (arm A and arm B)
Cognition impaired by 2 levels (HUI)	10	10	5 vs 16
Hearing loss 40dB at 4000Hz	10	10	5 vs 16
Cognition scored abnormal (HUI)	50	20	42 vs 64
SDQ score above screening threshold	50	20	42 vs 64
Growth failure	90	12	89 vs 102

For comparison of continuous variables such as the mean number of attributes scored as 'affected' (i.e.suboptimal) between the two treatment arms, transposition of the means and standard deviations reported in the study of French children with PNET  suggests that the HIT-SIOP PNET 4 study, with 106 ascertained surviving patients in each arm, would have the power to detect a mean difference of 0.6 between the numbers of attributes affected in the two treatment arms.

Analysis of binary outcome data will make use initially of chi-squared tests in order to compare the proportions of children with specific attributes in relation to baseline, treatment-related and demographic characteristics. Further analysis will make use of logistic regression techniques. When outcomes are ordinal (i.e. mild, moderate, severe) chi squared and chi-squared for trend tests will be used initially, and further analysis will make use of ordered polytomous regression techniques. For continuous outcomes variables initial analyses will make use of parametric, i.e. t-test, or non-parametric, i.e. Mann Whitney, as appropriate. Further analyses to explore the variability of outcome, possibly after suitable transformations will use multiple regression techniques.

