#### 4.7.3.1 Cross Sectional Data Collection

An additional cross sectional data collection point will be conducted starting in October 2010 to obtain a snap-shot of quality of survival data. It has been necessary to implement the collection of an additional set-of data because the quality of the data obtained so far from the longnitudial study has been poor and unanalysable. The question of quality of survival has

become even more crucial, as the emerging data suggests that there is no significant difference in event free survival between the treatment arms (Lannering, B., Rutowski, S., Doz, F., Pizer, B, Gustafsson, G., Navajas, A et al. (2010). HIT-SIOP PNET 4 – A randomised muticentre study of hyperfractaionated (HFRT) versus standard radiotherapy (STRT) in children with standard risk medulloblastoma. *Neuro-oncology*, *12*, ii5). The information obtained from the cross-section data collection will help to inform the upcoming PNET 5 and PNET 6 studies.

The assessments used in the cross-sectional data collection are listed in Appendix M.

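### Section 13.12 still rests 80% power for late effects on 213 ascertained survivors, was not reconciled with section 4.7.3.1, and overstates power in its two 10%-prevalence rows

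*Protocol*

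**What the plan says.** Section 13.12, under Secondary Endpoints relating to Outcome, starts from the planned arms: "The size of the groups in each of the two treatment arms is planned to be 160 children". It continues "Assuming event free survival of 75 % and 10 % loss of these survivors to follow-up", and heads its table with 213 ascertained survivors. The differences listed are those that the "treatment arms that the study would have 80 % power to detect at P<0.05 is". There are five rows:

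- HUI cognition impaired by two levels, and hearing loss: 10% overall prevalence, 10-point difference, 5 v 16 affected.
- HUI cognition abnormal, and SDQ above threshold: 50% prevalence, 20-point difference, 42 v 64.
- Growth failure: 90% prevalence, 12-point difference, 89 v 102.

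The continuous-outcome statement that follows also works "with 106 ascertained surviving patients in each arm". The opening of 13.12 still says: "The measures will provide a longitudinal, prospective description of Health Status and emotional health".

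Section 4.7.3.1 explains that an extra cross-sectional collection is needed because "the quality of the data obtained so far from the longnitudial study has been poor and unanalysable". It gives no response rate, no number to be approached and no power for that collection. Appendix M describes it as questionnaire booklets with largely unchanged content and altered age bands.

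**The concern.** Two parts of one protocol version describe the same data differently. Section 13.12 promises a longitudinal dataset with 10% loss and calculates power from it. Section 4.7.3.1 says that what has been collected longitudinally so far cannot be analysed. The power table was not revisited, and the added survey has no planning figure of its own.

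This matters because section 4.7.3.1 says the quality-of-survival question has gained importance, since emerging data suggest no significant EFS difference, and that the survey will inform successor studies. Section 13.12 treats the between-arm comparison of outcome as a main aim. A null late-effects result set beside a printed 80% power could be taken as reassurance that the protocol no longer supports. For the two 10%-prevalence rows, that reassurance was too strong even under the planning assumptions.

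**Working it through.** **Inputs (section 13.12).** 160 per arm; 75% event-free; 10% of survivors lost; 106 ascertained per arm; P<0.05, taken as two-sided because no side is stated; chi-squared test on proportions.

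**1. The number ascertained.** Event-free survivors: 320 × 0.75 = 240, or 120 per arm. Ascertained: 240 × 0.90 = 216. The table prints 213; the gap is trivial.

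**2. The table at its own 106 per arm.** With p̄ the mean of p1 and p2,

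power = Φ{ [ |p2 − p1|·√n − 1.96·√(2p̄(1−p̄)) ] / √(p1(1−p1) + p2(1−p2)) }, with √106 = 10.296.

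- 5% v 15%: (1.0296 − 1.96 × 0.4243)/0.4183 = 0.473, power **68%**. From the printed counts 5 v 16: **72%**.
- 40% v 60%: (2.0591 − 1.96 × 0.7071)/0.6928 = 0.972, power **83%**. From 42 v 64: 86%.
- 84% v 96%: (1.2355 − 1.96 × 0.4243)/0.4157 = 0.972, power **83%**. From 89 v 102: 85%.

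The 50% and 90% rows are therefore sound at n=213; the 10% rows are not. Other two-sided methods do not rescue them: unpooled variance, arcsine and exact power of the uncorrected chi-squared test reach at most about 75%, and a continuity correction lowers them further. A one-sided test gives the 10% rows 79-82%, but then the 50% rows have 90-92%. No single convention gives 80% throughout.

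**3. Symmetry.** A 10% and a 90% prevalence have the same variance, so they must share one detectable difference. At 106 per arm and 80% power it is about 11.5 points (12.5 with continuity correction). The table prints 10 for one and 12 for the other.

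**4. Numbers needed for 80% power.** n per arm = { [1.96·√(2p̄(1−p̄)) + 0.842·√(p1(1−p1)+p2(1−p2))] / (p2 − p1) }².

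- 40% v 60%: 97 per arm; 97/120 = 81% of expected survivors.
- 84% v 96%: also 97 per arm.
- 5% v 15%: 141 per arm, more than the 120 survivors expected.

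**5. Power if ascertainment differs from 90%.** The protocol gives no actual rate, so every row below is an assumption.

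| Share of 240 ascertained | Per arm | Power, 40% v 60% | 80%-detectable difference at 50% prevalence |
|---|---|---|---|
| 90% | 108 | 84% | 19 points |
| 80% | 96 | 80% | 20 points |
| 67% | 80 | 72% | 22 points |
| 40% | 48 | 50% | 28 points |

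**The case against.** The strongest reply is that nothing here shows that power has been lost. Section 4.7.3.1 speaks of the quality of data obtained so far and gives no follow-up rate. The survey is additional, was introduced to deal with this very problem, and keeps the HUI and SDQ booklets. If about 81% of expected survivors respond, the 40% v 60% rows are back at 80% power. Age-20 assessments were also still to come for younger patients. All of this stands. A reader might infer that the study does not have 80% power for HUI and SDQ, but the documents do not support that. They support only that the stated figure no longer has a basis.

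A reader might also infer that the hearing and growth figures should be withdrawn, because a booklet survey contains no audiogram or height measurement. That does not follow either. Section 13.12 does list endocrine and audiological data among the quality-of-survival studies. But those data arrive by separate routes: audiometry before each chemotherapy course and at the end of treatment (sections 4.7.6, 10.2.1 and 10.4.4), and growth and hormone Forms 9 and 10 (Appendix Q). No passage clearly says that those failed. What remains open is how many usable records they hold.

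Finally, section 13.8 makes secondary p-values explorative, and survey planning numbers could sit in a statistical analysis plan that is not shown. The first point limits the consequence. The second does not remove the problem, because the protocol itself prints the power figures and also undercuts their premise. Neither point touches the error in the 10% rows.

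**Conclusion.** The point holds in two parts.

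First, section 13.12 was not reconciled with section 4.7.3.1, so 80% power from 213 ascertained survivors is no longer supported for the questionnaire outcomes. The size of any shortfall cannot be determined from the protocol. The break-even for the HUI and SDQ 40% v 60% rows is about 97 per arm, and the 84% to 50% range in power rests on assumed ascertainment of 90% down to 40%.

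Second, and independently of any missing data, the two 10%-prevalence rows have about 68-72% power rather than 80% at the planned 106 per arm. This assumes a two-sided 5% test, as is usual where no side is stated.

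The consequence is moderate: these are secondary, explorative comparisons, and the primary EFS analysis is untouched.

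**What to change.** Restate the section 13.12 table by data source:

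- **HUI and SDQ rows:** give the number of survivors approached in the October 2010 survey, then power and the 80%-detectable difference over response rates of 40-90%. Bring the sentence promising a longitudinal description into line with section 4.7.3.1.
- **10%-prevalence rows:** print either the actual power for 5% v 15% (about 68% at 106 per arm) or the difference detectable with 80% power (about 11.5 points). State the side of the test and use one method for all rows, so that the 10% and 90% rows agree.
- **Hearing and growth rows:** keep them, and state the usable number from their own audiograms and forms.
- **Interpretation:** judge null late-effects results by confidence intervals set against the restated differences, not by the absence of significance.

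The cost is protocol wording and a recalculated table. The stated power becomes less favourable. No more patients are needed.

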### 13.8 Statistical analysis

The analysis follows the Intention to Treat principle. The main question for the whole cohort of patients and for the HIT group will be analysed in hierarchical order with the analysis of the total group of patients at the top of hierarchy i.e. the significant difference of EFS between both arms of RT for HIT patients can only be achieved if a significant difference of EFS has already been shown for the total group of patients. For the two interim analyses of the main question a significance level of 0.005 will be used in each case. For the final analysis of the main question a significance level of 0.04 will be used. The overall significance level will be equal to 0.05.

The p-value of the tests to answer the secondary questions below will be regarded as explorative.

Corresponding to the main question, the following null-hypothesis and statistical tests will be used:

1. Null hypotheses: The EFS between patients with HFRT and standard RT is not different for the whole group nor for the HIT patients. These hypotheses will be tested with a two-sided log-rank test. Patients will contribute with all their follow up time to the analysis. To illustrate the course of events, hazard and survival function (including the 2, 3 and 5-year survival) in both therapy arms will be estimated.

Corresponding to the secondary questions, the following null-hypotheses and statistical tests will be used:

- 2. Null hypotheses: The PFS and OS in patients with HFRT and standard RT is not different. These hypotheses will be tested with a two sided log-rank test. Patients will contribute with all their follow up time to the analysis. To illustrate the course of events hazard and survival function (including the 2, 3 and 5-year survival) in both therapy arms will be estimated.
- 3. Null hypothesis: The time to local tumour progression in patients with HFRT and standard RT is not different. This hypothesis will be tested with a two sided log-rank test. Patients will contribute with all their follow up time to the analysis. To illustrate the course of events hazard and survival function (including the 2,3 and 5-year survival) in both therapy arms will be estimated.
- 4. Null hypotheses: There is no difference in health status, behaviour, audiological toxicity and endocrinological late effects or quality of life in patients with HFRT compared to patients with standard RT.

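### The late-effects table in 13.12 claims 80% power for a 10-point difference at 10% prevalence; two-sided power is about 60–75%, and the mirror-image growth row lists 12 points

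*Protocol*

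**What the plan says.** Protocol 13.12, under Secondary Endpoints relating to Outcome, builds its late-effects power statement in three steps.

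- Group size: "The size of the groups in each of the two treatment arms is planned to be 160 children".
- Attrition: "Assuming event free survival of 75 % and 10 % loss of these survivors to follow-up". The table is headed "Outcome in ascertained survivors (n=213"), and the text on continuous outcomes works "with 106 ascertained surviving patients in each arm".
- Claim: the listed differences are those between "treatment arms that the study would have 80 % power to detect at P<0.05 is".

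The rows are:

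| Outcome | Overall prevalence | Difference | Affected, arm A vs B |
|---|---|---|---|
| Cognition, two-level impairment (HUI) | 10% | 10 points | 5 vs 16 |
| Hearing, 40 dB at 4000 Hz | 10% | 10 points | 5 vs 16 |
| Cognition, any abnormal score (HUI) | 50% | 20 points | 42 vs 64 |
| SDQ above threshold | 50% | 20 points | 42 vs 64 |
| Growth failure | 90% | 12 points | 89 vs 102 |

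On the test, the same section says: "Analysis of binary outcome data will make use initially of chi-squared tests". Sidedness is not printed beside the table. The hypotheses are non-directional in 13.12 ("We aim to test the hypothesis that treatment allocation influences cognition, hearing, behaviour, growth and/or reproductive health") and in 13.8 ("There is no difference in health status, behaviour, audiological toxicity and endocrinological late effects or quality of life").

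**The concern.** A chi-squared comparison of two proportions does not change when affected and unaffected are exchanged. At a fixed n, alpha and power, 10% and 90% prevalence must therefore have the same detectable difference. The table gives 10 points for one and 12 for the other, so at least one entry is wrong whatever software produced it.

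The stake is how the cognition and hearing comparisons are planned and read. 13.12 names these two first among its late-effect hypotheses, and 4.7.3.1 gives quality of survival more weight once emerging data suggested no significant EFS difference. The printed table implies a 20% chance of missing a true 10-point difference on these two outcomes. The actual chance is larger.

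**Working it through.** **Inputs (Protocol 13.12).** n = 106 per arm (213/2 = 106.5), chi-squared test, power claim 80% at P<0.05. I take 0.05 as two-sided because the hypotheses are non-directional. An overall prevalence of 10% with a 10-point difference means 5% vs 15%.

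**Formula (pooled normal approximation).** With p̄ = (p1 + p2)/2,

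power = Φ{ [ |p1 − p2| − 1.96·√(2p̄(1−p̄)/n) ] / √( [p1(1−p1) + p2(1−p2)]/n ) }.

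**Rows that reproduce.**

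- 40% vs 60%: (0.200 − 1.96 × 0.0687)/0.0673 = 0.97, so power is 83.4%.
- 84% vs 96%: (0.120 − 1.96 × 0.0412)/0.0404 = 0.97, so power is 83.4%.

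**Rows that do not.**

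- 5% vs 15%: (0.100 − 1.96 × 0.0412)/0.0406 = 0.47, so power is 68.2%.

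**Other two-sided methods, n = 106 per arm (power, %).**

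| Method | 5% vs 15% | Counts 5 vs 16 | 40% vs 60% | 84% vs 96% |
|---|---|---|---|---|
| Pooled normal | 68.2 | 71.8 | 83.4 | 83.4 |
| Unpooled normal | 69.2 | 72.8 | 84.4 | 84.4 |
| Normal, continuity-corrected | 59.5 | 63.5 | 79.7 | 77.0 |
| Arcsine | 70.8 | 74.6 | 83.4 | 86.4 |
| Exact, uncorrected chi-squared | 71.0 | 74.8 | 82.6 | 86.7 |
| Exact, continuity-corrected | 60.1 | 64.4 | 78.9 | 79.0 |
| Exact, Fisher | 61.9 | 66.1 | 78.9 | 80.3 |

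The printed counts are slightly more favourable than the nominal percentages because 5/106 = 4.7% and 16/106 = 15.1%, a gap of 10.4 points. They still reach at most about 75%.

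**Mirror check.** In the growth row, 89 vs 102 affected out of 106 is 17 vs 4 unaffected. That is the 10% prevalence problem with a 12-point difference. Solving for 80% power at n = 106 gives 11.5 points (12.4 with continuity correction) at both 10% and 90% prevalence. At 50% it gives 19.1 (20.1 corrected). The growth row and the 20-point rows agree with this; the 10-point rows do not.

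**Sample size for 10 points.** 5% vs 15% at 80% power needs 141 ascertained survivors per arm (160 with continuity correction), against about 106.

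**The printed n.** 320 × 0.75 × 0.90 = 216, or 108 per arm, not 213. Using 108 moves the pooled power for 5% vs 15% from 68.2% to 69.0%, so this small discrepancy does not explain the gap.

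**The case against.** **One-sided testing.** The table prints only P<0.05, and 13.8 names no test for the late-effects hypothesis. A one-sided 0.05 test gives 78.6% for 5% vs 15% and 81.5% for 5 vs 16, so it would be wrong to say that no version of the test reproduces these rows. It does not rescue the table, though. One-sided testing puts the 50% and 90% prevalence rows at about 90%, and it conflicts with the non-directional hypotheses. No single convention reproduces all five rows.

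**Importance.** This objection largely stands. 13.8 treats p-values for secondary questions as explorative. The target of 320 comes from the EFS simulation in 13.10, and the ototoxicity stopping rule in 13.7 uses HIT grades 3–4 with its own 20% limit. 13.4 defines audiological toxicity by the HIT grading in 10.4.4, so the 4000 Hz row is a planning scenario and not that endpoint. By version 3.0, 4.7.3.1 already describes the longitudinal data as unfit for analysis and adds a cross-sectional collection.

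**A smaller n.** A reader might carry the 13.10 hazards to five years (0.70^(5/3) = 0.552 and 0.85^(5/3) = 0.763, mean × 320 × 0.9 ≈ 189) and conclude that power is lower still. The document does not support that substitution. 13.12 states its own 75% EFS and ties it to no year, and the same hazards at three years give 320 × 0.775 × 0.9 ≈ 223, more than 213.

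**Reading of a null result.** A reader might also infer that a null result will be reported as excluding a 10-point difference. Nothing in the protocol says so, and the explorative label points the other way.

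**Conclusion.** The 80% power claim is wrong for the two rows at 10% prevalence. With about 106 ascertained survivors per arm and a two-sided 0.05 test, power is about 60–71% for 5% vs 15% and about 64–75% for the printed 5 vs 16. The chance of missing a difference of that size is therefore about 25–40%, against the stated 20%. The contradiction with the growth-failure row needs no choice of method: it follows from the symmetry of the test.

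The error stops there. The other three rows are consistent with roughly 80% power. The conclusion rests on the printed n, equal arms, and two-sided testing inferred from the non-directional hypotheses. Severity is moderate: the table misstates sensitivity for secondary, explorative outcomes and leaves the sample size and the EFS analysis untouched.

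**What to change.** In the 13.12 table, change the two-level cognition row and the hearing row to a 12-point difference (4% vs 16%, about 4 vs 17 affected), matching the growth-failure row. Alternatively, keep 10 points and state power of about 60–75% for those two rows. State that the test is two-sided. Leave the other rows as they are.

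The n of 213 may be corrected to 216, but this is cosmetic. Do not replace it with 189.

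The cost is two table rows and a few words. The stated sensitivity for severe cognitive impairment and hearing becomes slightly less favourable. No patients, assessments or analyses change.
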